#### **Duration of ICU stay**

The duration (number of days) of ICU stay from Day 1 through Day 29 will be calculated based on ICU admission and discharge dates recorded on the eCRF. Number of days in the ICU will be compared between treatment groups using an ANOVA model, including number of days in the ICU as a dependent variable and treatment group as a fixed effect. From this model, the LS means and 95% CIs for each treatment group, the treatment difference in the LS means, the 95% CI for the difference, and the associated p-value will be presented. If appropriate, an ANCOVA model may instead be used to additionally adjust for baseline characteristics such as age and gender.

In the event the data is highly skewed, e.g. very few subjects with ICU admissions, a sensitivity analysis using a non-parametric Wilcoxon Rank Sum test will be performed. The p-value from Wilcoxon Rank Sum test, as well as the Hodges-Lehmann estimate of the treatment difference and the corresponding 95% CI will be provided.

Subjects who died while in ICU will be assigned as in the ICU for the number of days remaining from the day of death to Day 29 for the analysis. Subjects who were at ICU at study completion will be assigned an ICU end date equals to the date of completion for the purpose of deriving number of ICU days. Subjects who are alive and never admitted into the ICU through Day 29 will be included in the analysis with a value of zero ICU days.

#### **Duration of any oxygen use**

The duration (number of Days) of any oxygen use from Day 1 through Day 29 will be calculated based on the start/stop date of using oxygen supplementation recorded on the eCRF All Visits page “General Duration of Hospitalization, & Overall Requirement for Mechanical Ventilation, ICU Admission and/or Oxygen Supplementation”. Number of days on oxygen will be compared between treatment groups using an analysis of variance (ANOVA) model, including number of days on oxygen as a dependent variable and treatment group as a fixed effect. From this model, the LS means and 95% CIs for each treatment group, the treatment difference in the LS means, the 95% CI for the difference, and the associated p-value will be presented. If appropriate, an analysis of covariance (ANCOVA) model may instead be used to additionally adjust for baseline characteristics such as age and gender.

Subjects who died during the hospitalization without a stop date of using oxygen supplementation recorded on the eCRF will be assigned as being on oxygen for the number of days remaining to Day 29 for the analysis. Subjects who had oxygen use ongoing at study completion will be assigned an oxygen use end date equals to the date of completion for the purpose of deriving duration of oxygen use. Subjects who never received supplemental oxygen through Day 29 will be included in the analysis with a value of zero days of oxygen use.

A listing of all supplemental oxygen and saturation ( $SpO_2$  and  $SaO_2$ ) data collected throughout the study will be provided.

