	GC2006-A Multicenter, Randomized, Open-label, Parallel Group Pilot Study to Evaluate the Safety and Efficacy of Prolastin®-C Liquid plus Standard Medical Treatment (SMT) versus SMT alone in Hospitalized Subjects with						Page	53 of 94

NaCl USP, or equivalent of commensurate volume to preserve the blind. If the subject has been discharged from the hospital at the time of the Day 8 blinded Liquid Alpha₁-PI (Human) or Placebo infusion, the 2nd infusion is not mandatory, and is at the discretion of the Principal Investigator and subject.

Coinciding with this time point, subjects who opt to receive the 2nd blinded infusion of Liquid Alpha₁-PI (Human) or Placebo will have levels of alpha 1-PI (AAT) activity and antigen measured on Day 8. Both plasma (sodium citrate) and serum samples are to be stored at -70° C for measurement of both antigenic content and functional activity (potency); for all such subjects, samples must be obtained *prior to* blinded Liquid Alpha₁-PI (Human) or Placebo infusion.

During study infusion on Day 8, vital signs will be measured immediately before the start of infusion, after the first 5 minutes of infusion, and subsequently at 5-10-minute intervals during infusion until the end of infusion. Vital signs will also be measured 2 hours after the end of study infusion.

Daily assessments include the following:

- Ordinal Scale assessment
- NEWS ([Appendix 2](#))
- Clinical features key symptoms: fever, cough, shortness of breath, fatigue, myalgia etc.
- Vital signs (temperature, systolic and diastolic blood pressure, pulse, respiratory rate)
- Record any supplemental oxygen administration (type, %, flow start/end date/time)
- If subject requires mechanical ventilation post randomization: Record mechanical ventilation (start/end date/time)
- Record oxygen saturation (specify on or off oxygen supplementation)
- If subject requires ICU admission post randomization: Record ICU admission date
- Record SAEs and TEAEs
- Record standard care concomitant medications

On Day 5 ± 1 day the following specimens will be obtained (mandatory assessments for all subjects with daily assessments for Day 5 detailed immediately above):

- Respiratory sample for quantitative measurement of SARS-CoV-2 viral load by NAT or PCR (real-time RT-PCR) (obtained via nasopharyngeal swab)

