Appendix 1 Schedule of Study Procedures

Study Period	Screen/ Baseline	IP	SMT and Daily Evaluations ^l										Follow-Up	Follow-Up Clinic Visit Day				
			2	3	4	5±1 ^m day	6	7	8	9	10	11-14 Daily if in hospital		15± 1 day ^m	16-28 Daily if in hospital	29 ^e ± 1 day ^m	Day 60 ± 2 days	Day 90 ± 2 days
Procedures/assessments	Study Day	1	1 st IP infusion day															
Informed consent		X																
Inclusion/exclusion criteria		X																
Demography, (including age [year of birth], gender, race, and ethnicity), disease characteristics (date of exposure, date of onset ^a)		X																
Pregnancy test ^b		X																
Ordinal Scale (at the 1 st assessment of a given day) ^c		X		X	X	X	X	X	X	X	X	X	X	X	X	X	X	
National Early Warning Score (NEWS) (Appendix 2)		X		X	X	X	X	X	X	X	X	X	X	X	X	X	X	
Clinical features key symptoms: fever, cough, shortness of breath, fatigue, myalgia etc.		X		X	X	X	X	X	X	X	X	X	X	X	X	X	X	
Vital signs (temperature, systolic and diastolic blood pressure, pulse, respiratory rate)		X	X ⁱ	X	X	X	X	X	X ⁱ	X	X	X	X	X	X	X	X	
Weight		X																
Record result of historical SARS-CoV-2 PCR (qualitative RT-PCR) or NAT or other commercial or public health assay approved by regulatory authorities as a diagnostic test for COVID-19 in any specimen during the current hospital admission OR 96 hours prior to the hospital admission date and prior to randomization (the SARS-CoV-2 test results must be performed by a hospital laboratory and the documentation available) (eligibility criterion)		X																

CONFIDENTIAL

GRIFOLS	Number	BIG-CL-PRT-00019	Version	6.0	Status	Effective	08-Dec-2021
	GC2006 -A Multicenter, Randomized, Open-label, Parallel Group Pilot Study to Evaluate the Safety and Efficacy of Prolastin®-C Liquid plus Standard Medical Treatment (SMT) versus						
Bioscience Industrial Group							81 of 94

Study Period	Screen/ Baseline	IP	SMT and Daily Evaluations^l									Follow-Up	Follow-Up Clinic Visit Day				
			2	3	4	5±1 ^m day	6	7	8	9	10		15± 1 day ^m	16-28 Daily if in hospital	29 ^e ± 1 day ^m	Day 60 ± 2 days	Day 90 ± 2 days
Study Day	1	1st IP infusion day															
Procedures/assessments																	
Record any supplemental oxygen administration (type, %, flow start/end date/time)	X		X	X	X	X	X	X	X	X	X	X	X	X	X		
If subject requires mechanical ventilation post randomization: Record any mechanical ventilation (start/end date/time)			X	X	X	X	X	X	X	X	X	X	X	X	X		

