### 2.2.2 Secondary Efficacy Endpoints

The secondary efficacy endpoints include the following:

- Assessment of Clinical Severity: Change in NEWS from baseline (Day 1 through Day 29).  
The NEWS has demonstrated an ability to discriminate patients at risk of poor outcomes. This score is based on 7 clinical parameters (respiration rate, oxygen saturation, any supplemental oxygen, temperature, systolic blood pressure, heart rate, level of consciousness [Alert, Voice, Pain, Unresponsive]).
- Time to clinical response: NEWS  $\leq 2$  maintained for 24 hours, Day 1 through Day 29
- Time to hospital discharge: defined as duration of hospitalization from Day 1 through Day 29
- If admitted to ICU post randomization: Duration of ICU stay through Day 29
- Duration of any oxygen use Day 1 through Day 29
- If requiring mechanical ventilation post randomization: Duration mechanical ventilation through Day 29
- Absolute value and mean change from baseline in the Ordinal scale Day 1 through Day 29  
The Ordinal scale is as follows:
  - 1) Death;
  - 2) Hospitalized, on invasive mechanical ventilation or extracorporeal membrane oxygenation (ECMO);
  - 3) Hospitalized, on non-invasive ventilation or high flow oxygen devices;
  - 4) Hospitalized, requiring supplemental oxygen;
  - 5) Hospitalized, not requiring supplemental oxygen;
  - 6) Not hospitalized, limitation on activities;
  - 7) Not hospitalized, no limitations on activities.
- Proportion (percentage) of subjects in each severity category of the 7-point Ordinal scale at Day 15 and Day 29
- Time to sustained normalization of temperature and proportion of subjects with normalization of fever at all time points, defined as temperature  $<36.6$  °C armpit,  $<37.2$  °C oral, or  $<37.8$  °C rectal sustained for at least 24 hours
- Number of subjects who develop Acute Respiratory Distress Syndrome (ARDS) through

Day 29

- Length of time to clinical progression through Day 29 (defined as the time to death, mechanical ventilation, or ICU admission)

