#### **Duration of mechanical ventilation**

The duration (number of days) on mechanical ventilation from Day 1 through Day 29 will be calculated based on the start/stop dates of mechanical ventilation recorded on the eCRF All Visits

page “General Duration of Hospitalization, & Overall Requirement for Mechanical Ventilation, ICU Admission and/or Oxygen Supplementation”. Number of days on mechanical ventilation will be compared between treatment groups using an ANOVA model, including number of days on mechanical ventilation as a dependent variable and treatment group as a fixed effect. From this model, the LS means and 95% CIs for each treatment group, the treatment difference in the LS means, the 95% CI for the difference, and the associated p-value will be presented. If appropriate, an ANCOVA model may instead be used to additionally adjust for baseline characteristics such as age and gender.

In the event the data is highly skewed, e.g. very few subjects on mechanical ventilation, a sensitivity analysis using a non-parametric Wilcoxon Rank Sum test will be performed. The p-value from Wilcoxon Rank Sum test, as well as the Hodges-Lehmann estimate of the treatment difference and the corresponding 95% CI will be provided.

Subjects who died during the hospitalization without a stop date of mechanical ventilation recorded on the eCRF will be assigned as being on mechanical ventilation for the number of days remaining to Day 29 for the analysis. Subjects who had mechanical ventilation ongoing at study completion will be assigned a mechanical ventilation end date equals to the date of completion for the purpose of deriving duration of mechanical ventilation. Subjects who are never placed on mechanical ventilation through Day 29 will be included in the analysis with a value of zero days on mechanical ventilation.

A listing of all mechanical ventilation and oxygen administration data collected throughout the study will be provided.

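### SAP 6.2 derives duration of any oxygen use from oxygen-supplementation dates alone, so whether ventilated days and ventilated deaths count depends on whether the oxygen record was closed at intubation.

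*SAP*

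**What the plan says.** SAP 2.2.2 names the endpoint "Duration of any oxygen use Day 1 through Day 29" and defines it no further. SAP 6.2 supplies the derivation: "any oxygen use from Day 1 through Day 29 will be calculated based on the start/stop date of using oxygen supplementation", taken from the eCRF All Visits page. Three rules follow in that subsection:

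- A subject who died in hospital is filled to Day 29 only if no oxygen stop date was recorded.
- Oxygen still in use at study completion ends on the completion date.
- A subject who never had supplemental oxygen scores zero.

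Ventilation dates appear in none of these. The next subsection has ventilator days "calculated based on the start/stop dates of mechanical ventilation recorded on the eCRF All Visits" page, the same page, and they feed only the ventilation endpoint.

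The protocol collects the two as separate items. The daily assessments in Protocol 7.2.3 list "Record any supplemental oxygen administration (type, %, flow start/end date/time" and, separately, "If subject requires mechanical ventilation post randomization: Record mechanical ventilation (start/end date/time". Appendix 1 gives them separate rows. The ordinal scale also separates the states: "Hospitalized, requiring supplemental oxygen" is category 4, and invasive ventilation or ECMO is category 2.

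**The concern.** A ventilated subject is receiving oxygen, so a reader would expect ventilated days to count towards any oxygen use. The SAP's rule does not secure this. Because oxygen and ventilation are separate items, a site could reasonably close the oxygen record at intubation. Another site could leave it open. The same clinical course then gets two different scores, and under one of them the sicker subject looks better.

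The death rule makes this worse. An oxygen stop date entered at intubation disables the fill to Day 29, so a ventilated death can receive one of the lowest values on a scale where low is good. The hospitalization and ICU rules in SAP 6.2 fill deaths to Day 29 without any such condition. SAP 4.4 announces a worst-case approach for selected continuous efficacy endpoints, with details in Section 6.

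At stake is the between-arm difference on an endpoint that has its own ANOVA p-value and is on the list of secondary outcomes assessed for futility in SAP 8.2.

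**Working it through.** The plan states no figure for this endpoint, so there is none to reproduce. The check has two parts.

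**1. Individual courses.** These are hypothetical. SAP 4.6 gives duration = end - start + 1.

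| Course | Oxygen record closed at intubation | Record left open | Union of oxygen and ventilation days |
|---|---|---|---|
| Cannula Days 1-20, never ventilated | not applicable | 20 | 20 |
| Cannula to Day 6, ventilator Days 6-20 | 6 - 1 + 1 = 6 | 20 - 1 + 1 = 20 | 20 |
| Oxygen Days 1-6, ventilator Days 6-15, oxygen Days 15-20 | 6 + 6 = 12 if episodes are summed; 20 if first start to last stop is used | 20 | 20 |
| Cannula to Day 6, dies on the ventilator on Day 15 | 6 (death fill not triggered) | 29 (no stop date, so filled) | 29 with the death fill |

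The third row shows a further gap: the SAP does not say whether separate oxygen episodes are summed or spanned.

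**2. Group level.** The documents give no rates, so every input here is an assumption:

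- 50 per arm, with 20% of placebo and 10% of active subjects ventilated
- 8 oxygen days on average if never ventilated
- intubation evenly spread over Days 2-8 (mean 5)
- 12 ventilator days on average
- 40% of ventilated subjects die in hospital and are filled to Day 29
- no oxygen days counted after the end of ventilation in survivors

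Let D be the active minus placebo difference in mean days; a negative D favours active. Let M be the mean score of a ventilated subject. Then D = -(0.20 - 0.10) x (M - 8).

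- Union (true oxygen days): M = 0.4 x 29 + 0.6 x (5 + 12) = 21.8, so D = -0.10 x 13.8 = -1.38. If ventilator time varies widely and is cut off at Day 29 (exponential with mean 12), M falls to about 20.8 and D is about -1.3.
- All records closed at intubation: M = 5, so D = -0.10 x (5 - 8) = +0.3.
- Half of the records closed: D is the midpoint of the two, (-1.3 + 0.3)/2 = -0.5.
- No records closed: D is unchanged at about -1.3.

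The sign changes when the share of closed records, q, satisfies (1 - q)M + 5q = 8, that is q = (M - 8)/(M - 5). This gives 13.8/16.8 = 0.82, or 12.8/15.8 = 0.81 with M = 20.8. Shrinkage begins with the first closed record; reversal needs about four in five.

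**Range.** More generally, the benefit is understated by (difference in ventilated share) x (mean days dropped per ventilated subject). For 20% versus 10% and 5-15 days dropped, that is 0.5 to 1.5 days. Over a wider assumed range, it runs from 0.05 x 5 = 0.25 days (10% versus 5% ventilated) to 0.20 x 24 = 4.8 days (30% versus 10%).

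**The case against.** The strongest reply is that the harm depends on a data-entry practice that the documents do not show. The eCRF and its completion instructions are not among them, and nothing says that sites enter an oxygen stop date at intubation. Some wording leans the other way. SAP 6.2 speaks of a single oxygen start/stop date but of ventilation dates in the plural. The source page records overall requirements, while SAP 6.1 takes modality from a separate Day 29 page. That fits one oxygen span which a change of modality would not close. NEWS in Protocol Appendix 2 also scores supplemental oxygen as yes or no, with no exception for ventilated subjects.

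A second reply is that any oxygen use may have been meant as supplementation only. The secondary objective separates oxygen dependency from new ventilatory support, and ventilation has its own duration endpoint.

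Third, the impact is small. The endpoint is one of many in a study without multiplicity adjustment. Ventilated subjects also show up in ventilation days, the ordinal scale and time to clinical progression. Futility rests on conditional power for the primary outcome plus an assessment of the secondary outcomes for which no threshold is given.

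Most of this stands and limits the claim. A reader might infer that the SAP excludes ventilated days and so rewards deterioration, or that a drug preventing ventilation would show no benefit here. The documents do not support either: no passage excludes ventilated days, and the loss occurs only where records are closed. The hints towards an open record are not conclusive, however, and separate ventilation reporting does not correct the oxygen estimate. If exclusion was intended, the SAP does not say so.

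**Conclusion.** The point holds as a derivation whose result depends on an unstated recording practice. SAP 6.2 uses oxygen dates alone, adds no ventilation dates, and makes the death fill conditional on a missing oxygen stop date. The same course can therefore score 6 or 20 days, and the same ventilated death 6 or 29.

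At group level, the between-arm difference can shrink or reverse. Under the assumed rates, about -1.3 days becomes -0.5 with half of the records closed and +0.3 with all closed. With none closed it does not change. These sizes rest entirely on assumed ventilation shares, durations and mortality; the dependence on recording practice does not.

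The consequence is limited to one secondary endpoint and its place in the futility review. The primary endpoint does not use this derivation. The SAP should be corrected because the change is nearly free, but the point does not threaten the trial's main conclusion.

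**What to change.** In SAP 6.2, replace the derivation with the following:

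- Count each calendar day from Day 1 to Day 29 once if the subject was on supplemental oxygen or on mechanical ventilation or ECMO, using the union of the oxygen and ventilation dates. This also settles how repeated episodes are handled.
- Apply the ongoing-use and zero rules to the union.
- For a subject who died in hospital while on oxygen or ventilation, fill to Day 29 whether or not an oxygen or ventilation stop date was entered at intubation or at death.
- State where ECMO days are taken from, since the schedule has no ECMO date item of its own.

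If ventilated days are meant to be excluded, rename the endpoint and state how ventilated subjects and deaths are scored.

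The cost is a short SAP edit and minor programming. Oxygen and ventilation dates are already on the same eCRF page. Where records stayed open throughout ventilation, the union gives the same day counts as the current derivation.

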#### **Duration of mechanical ventilation**

The duration (number of days) on mechanical ventilation from Day 1 through Day 29 will be calculated based on the start/stop dates of mechanical ventilation recorded on the eCRF All Visits

page “General Duration of Hospitalization, & Overall Requirement for Mechanical Ventilation, ICU Admission and/or Oxygen Supplementation”. Number of days on mechanical ventilation will be compared between treatment groups using an ANOVA model, including number of days on mechanical ventilation as a dependent variable and treatment group as a fixed effect. From this model, the LS means and 95% CIs for each treatment group, the treatment difference in the LS means, the 95% CI for the difference, and the associated p-value will be presented. If appropriate, an ANCOVA model may instead be used to additionally adjust for baseline characteristics such as age and gender.

In the event the data is highly skewed, e.g. very few subjects on mechanical ventilation, a sensitivity analysis using a non-parametric Wilcoxon Rank Sum test will be performed. The p-value from Wilcoxon Rank Sum test, as well as the Hodges-Lehmann estimate of the treatment difference and the corresponding 95% CI will be provided.

Subjects who died during the hospitalization without a stop date of mechanical ventilation recorded on the eCRF will be assigned as being on mechanical ventilation for the number of days remaining to Day 29 for the analysis. Subjects who had mechanical ventilation ongoing at study completion will be assigned a mechanical ventilation end date equals to the date of completion for the purpose of deriving duration of mechanical ventilation. Subjects who are never placed on mechanical ventilation through Day 29 will be included in the analysis with a value of zero days on mechanical ventilation.

A listing of all mechanical ventilation and oxygen administration data collected throughout the study will be provided.

### **Ordinal scales**

- a) The absolute value and change from baseline in the Ordinal scale from Day 1 through Day 29 will be summarized by treatment group and visit using descriptive statistics.

Mean change in Ordinal scales through Day 29 will be evaluated by fitting a linear MMRM similar to the one described above for “assessment of clinical severity.”

- b) The proportion of subjects in each severity category of the 7-point Ordinal scale at Day 15 and Day 29 will be tabulated. The difference in severity category distribution between treatment groups at Day 15 and Day 29 will be examined using proportional-odds cumulative logit model. The cumulative logits model will compare lower ordinal scales to higher ones, or equivalently, less favorable outcomes to more favorable ones. The model may be adjusted for baseline characteristics such as age and gender if appropriate. The estimated odds ratio and 95% CI will be presented. Graphical illustrations of the fitted model will also be presented for Day 15 and Day 29.

The proportional odds assumption will be tested using a score test at the two-sided alpha level of 0.05. If the proportional odds assumption is not satisfied, given the anti-conservative nature of the score test, the proportional odds model will still be used for the analysis, and the results will be presented along with the score test p-value to help put these results in context. If the proportion odds assumption is rejected or if the proportional odds model fails to converge, a sensitivity or alternative analysis using a non-parametric Wilcoxon Rank Sum test will be performed. The p-value from Wilcoxon Rank Sum test, as well as the Hodges-Lehmann estimate of the treatment difference and the corresponding

95% CI will be provided.

